6.2.4.1 Patient disposition and reasons for withdrawal

As of 28 March 2019 (data cut-off date, unclean data) a total of 57 patients have been screened in the ARMY-1 study, 47 of whom have been treated, all using the "*one-shot*" schedule of administration, as tabulated below. Patient disposition at the cut-off date is provided below:

Number of Patients	Cohort 0.1 mg/kg N=4	Cohort 0.3 mg/kg N=7	Cohort 0.6 mg/kg N=6	Cohort 1.0 mg/kg N=8	Cohort 1.7 mg/kg N=17*	Cohort 2.5 mg/kg N=5	Overall N=47
Screened	7	8	7	10	20	5	57
Screening failure	3	1	1	2	3	0	10
Safety population	4/(100.0%)	7/(100.0%)	6/(100.0%)	8/(100.0%)	17/(100.0%)	5/(100.0%)	47/(100.0%)
DLT population	3/(75.0%)	6/(85.7%)	6/(100.0%)	7/(87.5%)	7/(41.2%)	5/(100.0%)	34/(72.3%)
Efficacy population	2/(50.0%)	4/(57.1%)	5/(83.3%)	4/(50.0%)	5/(29.4%)	2/(40.0%)	22/(46.8%)
Early withdrawal	4/(100.0%)	7/(100.0%)	6/(100.0%)	8/(100.0%)	10/(58.8%)	5/(100.0%)	40/(85.1%)

Table 1: Patient disposition in the ARMY-1 study

Note: Percentages calculated using the total number of patients enrolled as the denominator * Includes 8 patients treated in the Step 2 of the study, all using the *"one-shot"* schedule

The majority of patients were early withdrawn from the study. The most frequently reported reason for withdrawal from study were disease progression and Investigator judgement (29.8% and 21.3%, respectively).

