6.2.4.2 Overview of safety

Using the "one-shot" schedule of administration, treatment-related TESS occurred in the majority (95.7%) of study patients: 44.7% and 36.2% of patients experienced grade \geq 3 treatment-related TESS and treatment-related serious TESS, respectively; the incidence of grade \geq 3 treatment-related TESS was clearly increased in the Cohort 2.5 mg/kg, in which all patients experienced such events; the 2.5 mg/kg dose level also retained the highest incidence of treatment-related serious TESS (60%). Moreover, in this latter dose level, 2 out of 5 patients experienced DLT events, hence leading to the stop of the dose escalation phase as well as to the definition of the immediately lower dose level, namely 1.7 mg/kg, as the MTD. Treatment-related deaths occurred in two patients overall (4.3%), one in Cohort 1.0 mg/kg and one in Cohort 1.7 mg/kg.

. Treatment-related TESS leading to temporary study drug administration interruption occurred in 63.8% of study patients; although there is not a clear dose-relationship for such events, the highest incidence was found in the 2.5 mg/kg dose level. The incidence of TESS leading to temporary study drug administration interruption and reported as serious ranged between 0 and 25.0% through all the cohorts, without a clear dose trend. The most frequently reported treatment-related grade < 3 TESS across all cohorts were *infusion*related reaction (38.3% of patients), disseminated intravascular coagulation (17.0%), chills (14.9%) and pyrexia (12.8%); while for the latter two types of TESS there was no dose trend, the incidence of disseminated intravascular coagulation was clearly higher in Cohort 2.5 mg/kg - 60.0% of patients experiencing such TESS - than in all the previous cohorts (0-17.6% of patients reported to experience such TESS). With regard to infusion related reaction, the highest incidence (75.0%) was found at the 0.1 mg/kg dose level, which however was run using the one hour infusion duration and without the standardized premedication encompassing the mandatory use of dexamethasone and

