8.4.7 Dosage modification and management of infusion toxicities

No dose adjustment is allowed.

The following instructions are provided for the management of infusion toxicities:

Toxicity	CTCAE v.4.03 Grade (duration)	Occurrence	Action on MEN1112 infusion	Action for toxicity
Cytokine release storm and/or Tumor lysis syndrome	3 (≤7 days)	First (during " ramp-up " administration)	 Interrupt MEN1112 until resolved to grade 0, then: If ≤20% of the ramp-up infusion dose (i.e. ≤50 mL of the total 250 mL infusion solution) was missed, restart MEN1112 at the next scheduled study drug administration. If >20% (i.e. >50 mL of the total 250 mL infusion solution) of the ramp-up infusion was missed, as soon as feasible (upon resolution to grade 0) restart MEN1112 to complete the residual ramp-up dose (e.g. if the dose was interrupted when 120 mL of the second ramp-up dose had been administered, complete the second ramp-up dose on the day after). If the infusion cannot be completed within 24 hours from dilution, a new infusion solution shall be prepared. If applicable, postpone the next scheduled study drug administration (i.e. the first infusion of the following 3-day ramp-up 	 Tumor lysis syndrome (TLS)¹: Consider multidisciplinary approach with involvement of nephrologists and intensive care physicians. Potassium must not be added to the hydration fluid. In the absence of contraindications, it is recommended rasburicase at a dose of 0·2 mg/kg/day (duration determined according to the clinical response) Symptomatic hypocalcaemia is recommended to be treated with a short infusion of calcium gluconate In patients with potassium levels ≥6 mmol/l or with ≥ 25% increase from baseline, cardiac monitoring is recommended Intractable fluid overload, hyperkalaemia, hyperuricaemia, hyperphosphataemia or

Confidential

Toxicity	CTCAE v.4.03 Grade (duration)	Occurrence	Action on MEN1112 infusion	Action for toxicity
			dosing) to ensure an interval of 5 days between any study drug administration is guaranteed.	hypocalcaemia are indications for renal dialysis.
				• Consider intensive care unit admittance for severe (grade 3-4) TLS cases
				Cytokine release storm ² : paracetamol and high dose steroids (dexamethasone) are recommended. Consider intensive care unit admittance for severe (grade 3-4) cases
				Disseminated intravascular coagulation (DIC) ³ :

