- Recording of AEs and change in concomitant medications

Visit 13-15/Day 16-18, one, two and three days after Visit 12

- Physical examination including vital signs
- PS evaluation
- Blood sampling for safety lab test (at 24h, 48h and 72 h after start of infusion)
- Recording of AEs and change in concomitant medications

CYCLE 2

Visit 16/Day 22, seven days after Visit 12

Prior to study drug administration

- Physical examination including vital signs
- Weight measurement
- PS evaluation
- Blood sampling for safety lab test
- •
- Blood sampling for PK

(pre-infusion)

- Bone marrow aspirate for morphologic assessment,
- Recording of AEs and change in concomitant medications
- Premedication (see §8.4.2)

Study drug administration

- Study drug administration, given as a 6h infusion with constant infusion rate
- Vital signs every 15 minutes during the first hour of study drug administration and at 15 minutes after end of infusion
- Blood sampling for PK (at the end of infusion)
- Recording of AEs and change in concomitant medications

Visit 17-19/ Day 23-25, one, two and three days after the completion of Visit 16, respectively

- Physical examination including vital signs
- PS evaluation
- Blood sampling for safety lab test
- Recording of AEs and change in concomitant medications

Visit 20/Day 29, seven days after the completion of Visit 16

Prior to study drug administration

- Physical examination including vital signs
- Weight measurement
- PS evaluation
- Blood sampling for safety lab test
- Blood sampling for PK (pre-infusion)
- Recording of AEs and change in concomitant medication
- Premedication (see §8.4.2)

Study drug administration

- Study drug administration, given as a 6h infusion with constant infusion rate
- Vital signs every 15 minutes during the first hour of study drug administration and at 15 minutes after end of infusion
- Blood sampling for PK
 at the end of infusion
- Recording of AEs and change in concomitant medications

Visit 21-23/Day 30-32, one, two and three days after the completion of Visit 20, respectively

- Physical examination including vital signs
- PS evaluation
- Blood sampling for safety lab test
- Recording of AEs and change in concomitant medications

Visit 24/Day 36, seven days after the completion of Visit 20

Prior to study drug administration

Physical examination including vital signs

- Weight measurement
- PS evaluation
- Blood sampling for safety lab test
- Blood sampling for PK (pre-infusion)

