8.5.3 Pharmacokinetic Evaluation

Blood samples for MEN1112 serum concentration measurements will be taken during Treatment phase and End of Treatment as depicted in § 14.2. If any interruption occurs during Cycle 1 and the 3^{rd} infusion of Cycle 2 (i.e. where the PK is evaluated), blood sampling for PK & exploratory tests will be taken at the time of each infusion interruption and just before each infusion resumption.

$\begin{array}{ll} C_{max} & \mbox{Maximum observed serum concentration.} \\ t_{max} & \mbox{Time to } C_{max}. \\ C_{last} & \mbox{Last quantifiable serum concentration.} \\ t_{last} & \mbox{Time to } C_{last}. \\ C_{trough} & \mbox{Pre-dose serum concentration.} \\ C_{avg} & \mbox{AUC from dose time to } \tau \mbox{ (i.e. dosing interval) divided by } \tau \end{array}$

k _e	Apparent terminal elimination rate constant, estimated by log- linear regression analysis on serum concentrations visually assessed to be on the terminal log-linear phase.
$t_{\frac{1}{2}}$	The terminal serum half-life, calculated according to the following equation: $t_{1/2} = \frac{0.693}{k_e}$
AUC _(0-t)	Area under the serum concentration-time curves from time zero (pre-dose) to the time of the last quantifiable concentration, calculated by means of the linear-log trapezoidal method.
$\mathrm{AUC}_{(0-\infty)}$	Area under the serum concentration-time curve from time zero to infinity, calculated according to the following equation: $AUC = AUC + \frac{C_{last}}{C_{last}}$
	$moc_{(0-\infty)} = moc_{(0-t)} + k_e$
%AUC _{ex}	The percentage of AUC _(0-∞) obtained by extrapolation calculated as follows: $AUC_{ex}(\%) = \frac{AUC_{(0-∞)} - AUC_{(0-t)}}{AUC_{(0-∞)}} \cdot 100$
CL	Systemic clearance, calculated according to the following equation: $CL = \frac{Dose}{AUC_{(0-\infty)}}$
V _{ss}	Volume of distribution at steady state, calculated according to the following equation: $V_{ss} = CL \cdot MRT$
V _d	Volume of distribution based on the terminal phase, calculated according to the following equation:
	$V_d = \frac{Dose}{k_e \cdot AUC_{(0-\infty)}}$
$AUMC_{(0-\infty)}$	The area under the first moment curve from zero to infinity calculated using the equation:
	$AUMC_{(0-\infty)} = \sum_{i=0}^{n-1} \frac{t_{i+1} - t_i}{2} (C_i t_i + C_{i+1} t_{i+1}) + \frac{tlast \cdot Clast}{k_e} + \frac{Clast}{k_e^2}$

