	$+\frac{t \cdot C_t}{\lambda_z} + \frac{C_t}{\lambda_z^2} + \frac{t \cdot C_t}{\lambda_z} + \frac{C_t}{\lambda_z^2} + \frac{t \cdot C_t}{\lambda_z^2} + \frac{C_t}{\lambda_z^2}$
MRT	Mean residence time (for drug given with a constant infusion rate over
	a period T _{inf}) was calculated as: $MRT = \frac{AUMC_{(0-\infty)}}{AUC_{(0-\infty)}} - \frac{T_{inf}}{2}$
Ro	Accumulation ratio calculated as: $Ro = \frac{1}{ 1 - e^{-k_c \tau} }$

PK parameters will be calculated, as data permit, following each of the three doses of the first *"ramp-up"* administration visit during Cycle 1 and following the third *"one-shot"* administration visit during Cycle 2.

The following PK variables will be assessed following the 1^{st} and 2^{nd} dose of the first *"ramp-up"* administration visit during Cycle 1:

• C_{max}, t_{max}, C_{trough}, C_{avg}, AUC_(0-t)

The following PK variables will be assessed following the 3^{rd} dose of the first "*ramp-up*" administration visit during Cycle 1:

C_{max}, t_{max}, C_{trough}, C_{avg}, C_{last}, t_{last}, AUC_(0-t), AUC_(0-∞), %AUC_{ex}, k_e, t_{1/2}, CL, V_{ss}, Vd, AUMC_(0-∞), MRT.

Total AUC following the first *"ramp-up"* administration visit during Cycle 1 will be calculated as the sum of $AUC_{(0-t)}$ related to each dose.

The following pharmacokinetic variables will be assessed following the 3rd "*one-shot*" administration visit during Cycle 2:

C_{max}, t_{max}, C_{trough}, C_{avg}, C_{last}, t_{last}, AUC_(0-t), AUC_(0-∞), %AUC_{ex}, k_e, t_{1/2}, CL, V_{ss}, Vd, AUMC_(0-∞), MRT, accumulation ratio (Ro).

Actual PK sampling times will be used in the derivation of PK parameters. Alternatively, it is also acceptable to consider the planned sampling times if they do not deviate by more than 5% from the actual. Planned sampling times may be used as a replacement for unknown or missing actual times. The calculation of the parameters listed above and others will depend upon the results of the drug concentration assay and the duration of drug infusions.

For the calculation of individual pharmacokinetic parameters, values Below the Lower Limit Of Quantification (BLLOQ) will be handled as follows:

- 1. BLLOQ values located before the t_{max} of their affiliating curve will be transformed to zero.
- If a BLLOQ value located after the t_{max} falls between two quantifiable concentrations, it will be omitted from the pharmacokinetic analysis.

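### MRT and Vss rest on a Tinf/2 correction that fits one constant-rate infusion, and no rule covers the interrupted doses that the protocol foresees

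*Combined protocol and SAP*

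**What the plan says.** Section 8.5.3 (Pharmacokinetic Evaluation) defines "Mean residence time (for drug given with a constant infusion rate over" a period Tinf, and states that it "was calculated as" AUMC(0-∞)/AUC(0-∞) − Tinf/2. The same section lists "Volume of distribution at steady state, calculated according to the following equation" Vss = CL × MRT, so any relative error in MRT passes to Vss unchanged. Both parameters are planned at two points: after the third dose of the first ramp-up, and after the third one-shot infusion of Cycle 2.

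The planned infusion meets the formula's condition (8.5.1: "Study drug administration, given as a 6h infusion with constant infusion rate"). Other sections provide for infusions that do not:

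- 8.5.3 adds PK samples during Cycle 1 and at the third Cycle 2 infusion, which "will be taken at the time of each infusion interruption and just before each infusion resumption".
- 8.4.7 calls for interruption at several grades of infusion toxicity. When more than 20% of a ramp-up infusion was missed, sites are to "as soon as feasible (upon resolution to grade 0) restart MEN1112 to complete the residual ramp-up dose". Its ramp-up example stops at 120 mL and finishes on the following day. Its one-shot example is 120 mL followed by 130 mL.
- 8.4.7 also prolongs the total infusion time to 8 hours after a drug-related interruption, on resumption and/or at later infusions.
- 8.4.2 covers resumption after two or more days, and the notes in 8.5.1 cover interruptions longer than 24 hours.

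No section defines Tinf for a split dose, gives another MRT formula, or removes interrupted profiles from the MRT and Vss summaries.

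**The concern.** The quantity to subtract from AUMC/AUC is the mean input time, that is, the average time at which drug enters the body. For one constant-rate infusion this is Tinf/2. For an interrupted dose it depends on how much was given before the stop, how long the pause lasted, and the rate in each segment.

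The text leaves two readings of Tinf open, running time and elapsed time from first start to final stop. They can give very different results for the same patient, so two analysts could both follow the plan and report different values. At stake are the cohort summaries of MRT and Vss. Section 6.2.4.3 already interprets Vss (as similar to blood volume) and reports large between-patient variability. An error that varies with split, pause length and half-life would add to that variability and blur comparisons between doses and schedules.

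**Working it through.** **The plan's figure on interruptions.** Section 6.2.4.2 reports that "Treatment-related TESS leading to temporary study drug administration interruption occurred in 63.8% of study patients". Table 1 in 6.2.4.1 gives 4 + 7 + 6 + 8 + 17 + 5 = 47 treated patients, and 30/47 = 63.8%, so the figure reproduces. The section says of the patients screened: "47 of whom have been treated, all using the" one-shot schedule.

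**Inputs.** Infusion volume 250 mL, planned duration 6 h, total running time after an interruption 8 h (8.4.7). Mean half-lives 10.8 to 41.8 h after a single dose and 12.8 to 146.4 h after repeat doses (6.2.4.3). Assumptions: a one-compartment linear model with volume 5 L, so true MRT = half-life/ln 2 = 15.6, 60.3 and 211.2 h at half-lives of 10.8, 41.8 and 146.4 h. The first segment runs at the 6 h rate and the second fills the 8 h total.

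**Formula.** Mean input time = sum over segments of (fraction of dose × segment midpoint). Error in MRT = mean input time − Tinf/2.

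**Base case.** For an uninterrupted 6 h infusion the mean input time is 3 h = Tinf/2, and the true MRT and Vss = 5.00 L are recovered. The formula is right where its condition holds.

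**The protocol's split, resumed 24 h after the start.**

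- First segment: fraction 120/250 = 0.48, from 0 to 0.48 × 6 = 2.88 h, midpoint 1.44 h.
- Second segment: fraction 0.52, duration 8 − 2.88 = 5.12 h, from 24 to 29.12 h, midpoint 26.56 h.
- Mean input time = 0.48 × 1.44 + 0.52 × 26.56 = 0.69 + 13.81 = 14.50 h.
- Running-time Tinf: 8/2 = 4 h, so MRT is 14.50 − 4.00 = 10.50 h too high.
- Elapsed-time Tinf: 29.12/2 = 14.56 h, error 14.50 − 14.56 = −0.06 h.

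On the running-time reading, 10.5/15.6 = +67% (Vss 8.37 L), 10.5/60.3 = +17% (5.87 L) and 10.5/211.2 = +5% (5.25 L).

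**Other splits, same method.** Resumption times are counted from the start of the infusion. The last column is the error in MRT and Vss at a half-life of 10.8 h.

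| Given before stop | Resumption | Mean input time (h) | Error, running Tinf (h) | Error, elapsed Tinf (h) | % running / elapsed |
|---|---|---|---|---|---|
| 120 mL | after 1 h pause | 4.04 | +0.04 | −0.46 | 0 / −3 |
| 120 mL | after 4 h pause | 5.60 | +1.60 | −0.40 | +10 / −3 |
| 120 mL | at 48 h | 26.98 | +22.98 | +0.42 | +148 / +3 |
| 50 mL | at 24 h | 22.04 | +18.04 | +6.64 | +116 / +43 |
| 195 mL | at 24 h | 7.47 | +3.47 | −6.19 | +22 / −40 |
| 195 mL | at 48 h | 12.75 | +8.75 | −12.91 | +56 / −83 |

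The 195 mL rows leave 55 mL (22%) missed, just above the 20% threshold, so the completion rule applies. At a half-life of 146.4 h the errors for next-day or later completion lie between −6% and +11%. Subtracting the mean input time returned the true MRT and Vss = 5.00 L in every row.

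**The case against.** The strongest reply is that section 8.5.3 states the constant-rate condition, calculates parameters only so far as the data allow, and makes the calculation depend on infusion duration. Section 9.5 leaves analysis detail to an SAP that is finalised before database lock. On that view nothing is misapplied; a detail is still to come. This stands in part, since the formula is correct under its own condition. But these statements supply no rule for when the condition fails, and the protocol arranges extra sampling for exactly that case.

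A reader might infer that 63.8% of patients, or most of them, would have a wrong MRT. The documents do not support this. The figure counts an interruption at any infusion under the one-shot schedule, not at the two profiled infusions under ramp-up. One cohort in it (0.1 mg/kg) used one-hour infusions without the later premedication. The ramp-up was introduced to prevent or limit such events. The documents give neither the number of pauses at the profiled infusions nor their length, and section 8.4.2 also foresees same-day resumption, where a short pause hardly matters.

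A reader might also infer that Tinf/2 is always wrong after an interruption. It is not: with elapsed time, a split that is nearly symmetric about its midpoint gives almost no error, as the protocol's own example shows.

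Finally, the check uses a linear model, while sections 6.2.4.3 and 6.3 describe more-than-proportional exposure and target-mediated disposition. That limits what any MRT-based Vss can mean. It does not justify subtracting the wrong input time.

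**Conclusion.** The point holds as a gap with a calculable effect. For doses completed the next day or later, the written rule is ambiguous, and under at least one reading of Tinf it can be materially wrong. In the protocol's own split resumed at 24 h, the running-time reading overstates MRT and Vss by 67%, 17% and 5% at half-lives of 10.8, 41.8 and 146.4 h, and the elapsed-time reading is close to unbiased. Asymmetric splits are biased under both readings. A 1 h same-day pause costs about 3% or less.

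The percentages rest on the one-compartment assumption and the 8 h running time. The errors in hours follow from the infusion timing alone. How many profiles would be affected cannot be derived from the documents. AUC, CL, half-life, DLT and MTD do not use this correction, and MRT and Vss are secondary, descriptive parameters, so this is a minor improvement rather than a threat to the trial's conclusions.

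**What to change.** In section 8.5.3 and the SAP, replace Tinf/2 by the dose-weighted mean input time: the sum over infusion segments of the fraction of the dose given times the segment midpoint, measured from the start of the infusion and taken from recorded start and stop times and volumes. It equals Tinf/2 when there is no interruption, so uninterrupted profiles do not change, and the running-or-elapsed question disappears. Where segment times or volumes are not available, exclude that profile from the MRT and Vss summaries by a rule set in advance, and report how many were excluded.

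The cost is slightly more analysis work and capture of segment volumes. Section 8.3.3 has the administered amount documented in the e-CRF, and 8.5.3 samples at each stop and resumption, but no section says that the volume given in each segment is recorded. The change removes the input-time error only; it does not guarantee a true Vss under target-mediated, non-linear disposition.

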- Blood sampling for PK (pre-infusion)
- Recording of AEs and change in concomitant medications
- TLS risk assessment (see Appendix I: TLS Manual for Investigator)
- TLS prophylaxis (see Appendix I: TLS Manual for Investigator)
- Premedication (see §8.4.2)

Study drug administration

- Study drug administration, given as a 6 h infusion with constant infusion rate
- Blood sampling for safety lab test at following time points after start of infusion: 2h, 4h, 8h, 12h.
- Vital signs every 15 minutes during the first hour of study drug administration and then at the same time points of blood sampling for safety lab test

- 12-lead ECG at the end of infusion
- Blood sampling for PK (at the end of infusion, and 6h after the end of infusion)
- Recording of AEs and change in concomitant medications

Visit 2/Day 2(one day after the completion of Visit 1) and Visit 3/Day 3 (one day after the completion of Visit 2)

Prior to study drug administration

- Physical examination, including vital signs
- PS evaluation
- 12-lead ECG
- Blood samplingfor safety lab test
- Blood sampling for PK (pre-infusion)
- Recording of AEs and change in concomitant medications
- TLS prophylaxis (see *Appendix I: TLS Manual for Investigator*)
- Premedication (see §8.4.2)

Study drug administration

- Study drug administration, given as 6h infusion with constant infusion rate
- Blood sampling for safety lab test at the following time points after start of infusion: 2h, 4h, 8h, 12h
- Vital signs every 15 minutes during the first hour of study drug administration and then at the same time points of
 - blood sampling for safety lab test
- 12-lead ECG at the end of infusion
- Urine collection at the end of infusion (ONLY at Visit 3)
- Blood sampling for PK
 at the end of infusion, 6h after the end of infusion (ONLY at Visit 2), 14h after the end of infusion (ONLY at Visit 3)
- Recording of AEs and change in concomitant medications

Visit 4/Day 4, one day after the completion of the entire first *"ramp-up"*

- Physical examination, including vital signs
- PS evaluation
- Blood sampling for safety lab test
- •
- Blood sampling for PK infusion

24h after the end of last "ramp-up" dosing

Bone marrow aspirate for morphologic assessment,

Recording of AEs and change in concomitant medications

Visit 5-6/Day 5-6, one and two days after Visit 4, respectively

- Blood sampling for PK
 (44h and 68h after the end of last "*ramp-up*" dosing infusion)

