- Recording of AEs and change in concomitant medications
- Premedication (see §8.4.2)

Study drug administration

- Study drug administration, given as a 6h infusion with constant infusion rate
- Vital signs every 15 minutes during the first hour of study drug administration and at 15 minutes after end of infusion
- Blood sampling for PK (at the end of infusion and at 1h and 6h after the end of infusion)
- Recording of AEs and change in concomitant medications

Visit 25-27/Day 37-39, one, two and three days after the completion of Visit 24, respectively

- Physical examination including vital signs
- PS evaluation
- Blood sampling for safety lab test including pregnancy test (only at Visit 27, if applicable)
- Blood sampling for PK (24h, 48h and 72h after the end of infusion)
- Recording of AEs and change in concomitant medications

Visit 28-29/Day 40-41, one and two days after Visit 27, respectively

- Blood sampling for PK (96h and 120h after the end of infusion)
- Recording of AEs and change in concomitant medications

Visit 30/Day 42, the day after Visit 29

- Physical examination including vital signs
- PS evaluation
- Blood sampling for safety lab test
- . .
- Blood sampling for PK

(144h after the end of infusion)

- Bone marrow aspirate for morphologic assessment,
- Recording of AEs and change in concomitant medications

NOTES:

- During Cycle 1, under the *"ramp-up"* dosing scheme, an administration visit will encompass the three *"ramp-up"* infusions (to be split in up to four days, in case of specific infusion-related toxicities, see §8.4.7) to complete the administration of MEN11112.
- Prior to start MEN1112 infusion, results of the safety lab tests (including hepatic function tests) should be duly checked by the Investigator to confirm that eligibility criteria are met (Visit 1/Day 1, prior of infusion) or no treatment withdrawal/dose interruption criteria are met (any subsequent infusion).
- One of the following adjustments is allowed:
 - +1 day for any "*ramp-up*" administration visit in case of WBC count $>10 \times 10^{9}$ /L on the first day of such visit, in order to lower the WBC count using hydroxyurea. This is applicable also to the "*one-shot*" infusion visit of Cycle 1 (Visit 12/Day 15).
 - + 1 day for each study drug administration visit (i.e. first *"ramp-up"* and *"one-shot"* administration visit).

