- In case of study visit re-schedule due to infusion related toxicities (see §8.4.7), WBC count recovery, or any other reasons, the interval of 5 days (Cycle 1) or 7 days (Cycle 2) between the end of any study drug administration visit and the start of the following one should be guaranteed.
- Moreover, at each infusion during the study conduct, in case of interruption due to drugrelated toxicities:
 - The infusion duration will be prolonged **constant infusion rate**; this infusion duration will then be applied to every subsequent infusions.
 - In case the interruption lasts >24 hours, the safety assessments will be repeated when the infusion is resumed according to the time-points scheduled for the original visit.
 - If any interruption occurs during Cycle 1 and the 3rd infusion of Cycle 2, blood sampling for PK & exploratory tests will also be taken at the time of each infusion interruption and just before each infusion resumption.
- During Cycle 1, under the "ramp-up" dosing scheme, prior to start each administration visit WBC count should be ≤ 10 x 10⁹/L. In case the "ramp-up" administration visit is split due to infusion-related toxicities, WBC count should be ≤ 10 x 10⁹/L also prior to start the second part of the "ramp-up" administration visit.
- During Cycle 1, patients must be treated and monitored as in-patients up to at least 24 hours after each study drug administration visit.
- As the consumption of fibrinogen is a marker of disseminated intravascular coagulation, the Investigator shall carefully monitor the fibrinogen decrease rate and consider prompt

treatment with fresh frozen plasma even in the presence of fibrinogen values within normal range.

END of TREATMENT

Visit 31-34/Day 43/50/57/64, one week, two weeks, three weeks and four weeks after Visit 24, respectively)

- Blood sampling for PK
- Blood sampling for immunogenicity assessment (ONLY at Visit 34)
- Recording of AEs and change in concomitant medications

NOTE: During the End of Treatment, a time-frame of + 1 day is allowed at any visit, however the scheduled time of the following visits should be maintained.

FOLLOW-UP PERIOD

Visit 35-38/Day 65/85/121/149, one, twenty-nine, fifty-seven and eighty-five days after Visit 34, respectively

- Physical examination, including vital signs
- PS evaluation
- Blood sampling for safety lab test including pregnancy test (if applicable)

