- Bone marrow aspirate for morphologic assessment on Visit 35 and Visit 37 only in patients showing peripheral blood labs consistent with CR/CRi/PR
- Recording of AEs and change in concomitant medications.

NOTES:

- To serve the best interest of the patients, for those achieving at least a partial remission, the Sponsor commits to consider providing MEN1112 to allow the prosecution of the infusions at the frequency recommended by the iDSMB on an individual basis and after discussion with the treating Investigator and the Medical Monitor. In this case, premedication and safety assessments will resemble those already described for study drug administration visits, unless differently advised by the iDSMB.
- During Follow-up Period, a time-frame of + 2 days each is allowed at any visit, however the scheduled time of the following visits should be maintained.

END OF STUDY

End of Study Visit (180 days after Visit 1/Day 1)

- Physical examination and vital signs
- PS evaluation
- Blood sampling for safety lab test including pregnancy test (if applicable)
- .

- Bone marrow aspirate for morphologic assessment,
- Recording of AEs and change in concomitant medications

NOTES:

- At the End of Study Visit, a time-frame of + 5 days is allowed.
- All patients shall undergo the End of Study Visit at the scheduled date or at the time of study withdrawal. Unscheduled assessments showing disease progression and leading to patient's withdrawal can replace the End of Study Visit provided that all assessment/procedures scheduled for this visit are completed.
- In case the patient is discontinued from the study within the treatment period, the End of Study Visit bone marrow aspirate is highly recommended to be performed.

GENERAL NOTES:

- For each safety lab test, blood sampling for PK (except for those to be collected at the end of infusion) and for vital signs, a window of +/- 5% of the required time interval is allowed.
- The total dose calculated for the first study drug administration can be applied also for the following ones providing that actual patient's weight is within ±10% of the weight measured prior to the first study drug administration; otherwise, the total dose to be given shall be calculated based on the weight measured at the corresponding visit.

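### Section 8.5.3 lets recorded PK sampling times be replaced by planned times within 5%, which adds avoidable error, usually small, to half-life and related parameters

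*Combined protocol and SAP*

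**What the plan says.** Section 8.5.3 opens with a clear rule: "Actual PK sampling times will be used in the derivation of PK parameters". Two relaxations follow. The first covers times that are known: "Alternatively, it is also acceptable to consider the planned sampling times if they do not deviate by more than 5% from the actual". The second covers times that are not: "Planned sampling times may be used as a replacement for unknown or missing actual times". No text says when the first option is to be used, by whom, or for which patients, and the second has no limit.

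The General Notes of section 8.5.1 (repeated in the synopsis) say that, for timed PK samples, "a window of +/- 5% of the required time interval is allowed". End-of-infusion samples are exempt. Visits 31–34 have their own rule: "During the End of Treatment, a time-frame of + 1 day is allowed at any visit".

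In Cycle 1 the last samples are taken "44h and 68h after the end of last" ramp-up infusion, after samples at 14 h and 24 h. After the third Cycle 2 infusion they are taken "24h, 48h and 72h after the end of infusion", then at 96, 120 and 144 h and at 1 to 4 weeks (Appendix II). Section 8.5.3 estimates ke by log-linear regression on points chosen by eye and sets no minimum number of points.

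**The concern.** Whether a planned time lies within 5% of the actual time can be checked only if the actual time is known. The option therefore never rescues missing data; it can only replace a known time by a less accurate one. Two sets of PK parameters from the same samples would both comply with the protocol.

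The tolerance is relative, so in hours it is widest on the late samples that can determine the terminal slope: 5% of 96, 120 and 144 h is 4.8, 6.0 and 7.2 h. Half-life comes directly from ke, and AUC to infinity, CL, Vd, Vss, MRT and Ro all use it in some way. The independent board sees PK data before each escalation (section 8.4.3.1), in small cohorts where one patient's error is hardly averaged out.

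**Working it through.** The documents state no timing-error figure, so there is none to reproduce.

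**Do the two 5% rules coincide?** Nearly. The sampling window is relative to the planned interval, the substitution rule to the actual time. For a 24 h sample the window is 22.8–25.2 h, while substitution is allowed from 24/1.05 = 22.86 h. A sample at 22.8 h is in window but deviates by 1.2/22.8 = 5.3%. For planned time p, both rules hold when the actual time lies between p/1.05 and 1.05p.

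**Effect on ke and half-life.** Assume error-free mono-exponential decline, with samples taken at actual times a but regressed on planned times p. Then

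estimated ke / true ke = Σ(p − p̄)a / Σ(p − p̄)²,

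and the half-life ratio is its inverse. The longest half-life arises when early points are late and late points early.

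- 44/68 h: (68/1.05 − 44 × 1.05)/24 = (64.76 − 46.20)/24 = 0.773; half-life × 1.293.
- 96/120/144 h: the middle point has zero weight, so (144/1.05 − 96 × 1.05)/48 = (137.14 − 100.80)/48 = 0.757; half-life × 1.321.
- 24–144 h, six points: 9206.4/10080 = 0.913; half-life × 1.095.

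The SDs below come from 100,000 simulated sets of independent deviations, uniform over the allowed range.

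| Points fitted (h) | Worst half-life error | SD |
|---|---|---|
| Cycle 1: 24, 44, 68 | −9.7% to +11.7% | 4.7% |
| Cycle 1: 14, 24, 44, 68 | −8.0% to +9.3% | 3.5% |
| Cycle 1: 44, 68 only | −18.6% to +29.3% | 9.8% |
| Cycle 2: 24 to 144 (six points) | −8.2% to +9.5% | 2.8% |
| Cycle 2: 96, 120, 144 | −19.7% to +32.1% | 10.5% |
| Cycle 2: 120, 144, 168 | −22.7% to +41.2% | 12.7% |

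As a hand check on 96/120/144 h, a uniform ±5% deviation has SD 0.05/√3 = 0.0289. The SD of the ke error is then 0.0289 × √(96² + 144²)/48 = 0.104, in line with the simulation. Half-life errors above 25% occur in 1.6% of draws for that fit, 0.7% for 44/68 h and none for 24/44/68 h. If all samples deviate by the same percentage, the error is about 5%.

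**Other parameters.** The section 8.5.3 formulas were applied with a 6 h infusion and a dosing interval of 168 h for Ro. The largest absolute errors for two Cycle 1 fits, at half-lives of 10.8 / 25 / 41.8 h (the ends are the single-dose range in section 6.2.4.3; 25 h is an assumed middle value), are:

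| Parameter | 44/68 h | 24/44/68 h |
|---|---|---|
| AUC to infinity | 1.7 / 5.4 / 11.0% | 2.9 / 4.2 / 6.0% |
| CL | 1.7 / 5.1 / 9.9% | 2.8 / 4.1 / 5.6% |
| Vss | 2.6 / 10.7 / 11.0% | 3.1 / 6.0 / 5.3% |
| Vd | 29 / 23 / 17% | 13.3 / 9.5 / 6.4% |
| MRT | 4 / 17 / 23% | 5.1 / 8.2 / 10.5% |
| Ro | 0 / 1.8 / 6.1% | 0 / 0.6 / 2.3% |

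The most extreme Cycle 2 case run is a 96/120/144 h fit at half-life 146.4 h (top of the repeat-dose range) with the profile ending at 144 h, so that 48% of the AUC is extrapolated. It gives AUC to infinity 18.3%, CL 15.5%, Vss 9.7%, Vd 12.0%, MRT 29% and Ro 21%.

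**Missing times.** At 1 week, a visit one day late is off by 24/168 = 14.3% of planned time, or 24/192 = 12.5% of actual. If the time is recorded, the 5% rule forbids substitution. If it is missing, planned time may still be used. At half-life 146.4 h that concentration would be filed 1 − 2^(−24/146.4) = 11% too low.

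**The case against.** The strongest reply is that little depends on this. Actual times are already the default. PK is a secondary objective, summarised descriptively by cohort (section 9.3.3) with no test planned. Escalation and the MTD follow DLT counts (section 8.4.3). Between-patient variability is described as large (section 6.2.4.3), and the mean bias in half-life from independent deviations is about 1% in these fits. Section 9.5 leaves analysis detail to a SAP still to be finalised. All of this stands, and it makes the point minor. It does not give the sentence a purpose.

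A reader might also infer something stronger: that every ke-based parameter can be wrong by 25–30%. The documents do not support that. Errors of this size need a fit on two points or on closely spaced late points, with first and last samples at opposite limits. Parameters that use ke only through the extrapolated tail move far less. Nor does every in-window sample qualify for substitution: the denominators differ, end-of-infusion samples are outside the window rule, and a full day's delay at 1 or 2 weeks exceeds 5%.

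**Conclusion.** The point holds as a minor improvement. The protocol permits known sampling times to be replaced by less accurate ones for almost every in-window timed sample up to 144 h, with no benefit. In ordinary fits the half-life error has SD about 3–5% and a worst case of about 9.5–12%; in extreme fits it approaches or passes 30%. Half-life carries the full ke error. Vd carries most of it at short half-lives, and MRT does when much of the AUC is extrapolated. AUC to infinity, CL, Vss and, at short half-lives, Ro carry much less.

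These sizes assume mono-exponential decline, no assay error and independent deviations spread over the whole window. Deviations actually seen may well be smaller; the documents give no data on them. The primary endpoint is not touched.

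**What to change.** In section 8.5.3, or in the SAP, delete the sentence beginning with Alternatively and derive all PK parameters from actual times whenever they are recorded. Keep planned times for by-time-point summaries. Where the clock time is missing but the visit date is known, use the recorded date. Flag samples that cannot be placed within the sampling window and leave them out of the ke regression.

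The error from this source then becomes zero for every sample with a recorded time. The cost is a short text change and the loss to ke of a few samples with unknown times. Section 9.5 allows minor deviations that leave the primary endpoint and analysis unchanged to be detailed in the SAP alone, so a substantial amendment appears unnecessary.
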